### **8.3.12 Safety data to be collected following the final DCO of the study**

For patients continuing to receive study treatment after final DCO and database closure, it is recommended that the patients continue the scheduled site visits and the investigators monitor the patients' safety laboratory results prior to and periodically during treatment with durvalumab in order to manage AEs in accordance with the durvalumab Toxicity Management Guidelines (see Section 8.4.5.1). The most current version of the Toxicity Management Guidelines is also available through the following link: <https://tmg.azirae.com>. All data after the final DCO and database closure will be recorded in the patient notes but will not otherwise be reported for the purposes of this study, with the exception of SAEs.

All SAEs that occur in patients still receiving durvalumab treatment (or within the 90 days following the last dose of durvalumab treatment) after the final DCO and database closure must be reported as detailed in Section 8.3.2.

### **8.3.13 Adverse events of special interest**

An adverse event of special interest (AESI) is one of scientific and medical interest specific to the understanding of the Investigational Product (IP) and may require close monitoring. An AESI may be serious or non-serious. The rapid reporting of AESIs allows ongoing surveillance of these events in order to characterize and understand them in association with the use of this IP.

#### **8.3.13.1 Adverse events of special interest for durvalumab**

AESIs for durvalumab include, but are not limited to, events with a potential inflammatory or immune-mediated mechanism and which may require more frequent monitoring and/or interventions such as steroids, immunosuppressants, and/or hormone replacement therapy. These AESIs are being closely monitored in clinical studies with durvalumab monotherapy and combination therapy. An immune-mediated adverse event (imAE) is defined as an AESI that is associated with drug exposure and is consistent with an immune-mediated mechanism of action (MOA) and where there is no clear alternate etiology. Serologic, immunologic, and histologic (biopsy) data, as appropriate, should be used to support an imAE diagnosis. Appropriate efforts should be made to rule out neoplastic, infectious, metabolic, toxin, or other etiologic causes of the imAE.

If the Investigator has any questions with regard to an event being an imAE, the Investigator should promptly contact the Study Physician. AESIs observed with anti PD-L/PD-1 agents such as durvalumab include pneumonitis, hepatitis, diarrhea/colitis, intestinal perforation, endocrinopathies (hypo- and hyper-thyroidism, adrenal insufficiency, hypophysitis/hypopituitarism and Type 1 diabetes

mellitus), nephritis, rash/dermatitis, myocarditis, myositis/polymyositis, pancreatitis and rare/less frequent imAEs including neuromuscular toxicities such as myasthenia gravis and Guillain-Barre syndrome.:

Other inflammatory responses that are rare/less frequent with a potential immune-mediated etiology include, but are not limited to, pericarditis, sarcoidosis, uveitis and other events involving the eye, and skin, hematological, rheumatological events, vasculitis, non-infectious meningitis and non-infectious encephalitis. It is possible that events with an inflammatory or immune mediated mechanism could occur in nearly all organs.

In addition, infusion-related reactions and hypersensitivity/anaphylactic reactions with a different underlying pharmacological etiology are also considered AESIs.

Further information on these risks (eg, presenting symptoms) can be found in the current version of the durvalumab IB. More specific guidelines for their evaluation and treatment are described in detail in the Dosing Modification and Toxicity Management Guidelines (see Section 8.4.5.1). These guidelines have been prepared by the Sponsor to assist the Investigator in the exercise of his/her clinical judgment in treating these types of toxicities. These guidelines apply to AEs considered causally related to the study drug/study regimen by the reporting Investigator.

**8.3.13.2 Any event of AESI should be reported to AstraZeneca Patient Safety, whether it is considered a non-serious AE or SAE and regardless of the Investigator's assessment of causality. These AEs must be reported according to the timelines for reporting an SAE to allow for timely safety monitoring. Adverse events of special interest for olaparib**

AESIs for olaparib comprise the important identified risk of MDS/AML and the important potential risks of:

- new primary malignancy (other than MDS/AML)
- pneumonitis

Any event of MDS/AML, new primary malignancy, or pneumonitis should be reported to AstraZeneca Patient Safety whether it is considered a non-serious AE (eg, non-melanoma skin cancer) or SAE, and regardless of Investigator's assessment of causality. These AEs must be reported according to the timelines for reporting an SAE (see Section 8.4.1) to allow timely safety monitoring.

### 8.3.13.3 Pneumonitis

If new or worsening pulmonary symptoms (eg, dyspnea or cough) or radiological abnormalities occur in the absence of a clear diagnosis, an interruption in study treatment dosing is recommended, and further diagnostic workup should be performed to exclude pneumonitis. The differential diagnosis should include the possibility of both immune-related and non-immune-related processes. AEs of pneumonitis are of interest for AstraZeneca as pneumonitis has been observed with use of anti-PD-1 mAbs (although not with anti-PD-L1 mAbs), and instances of pneumonitis have been reported in patients undergoing olaparib treatment.

Initial workup should consider the inclusion of a clinical evaluation, high-resolution CT scan, ruling-out infection, pulse oximetry, and other appropriate laboratory workup. Pulmonary consultation is highly recommended. Guidelines for the management of patients with immune-related AEs including pneumonitis are provided in the Dosing Modification and Toxicity Management Guidelines (see Section 8.4.5.1).

Following investigation, if no evidence of abnormality is observed on CT imaging and symptoms resolve, then study treatment can be restarted, if deemed appropriate by the Investigator. If significant pulmonary abnormalities are identified, these need to be discussed with the Study Physician.

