### **2.2.2 Durvalumab**

Durvalumab (MEDI4736, Imfinzi™) is a human mAb of the immunoglobulin (Ig) G1 kappa subclass that blocks the interaction of PD-L1 (but not programmed cell death ligand 2 [PD-L2]) with PD-1 on T cells and CD80 (B7.1) on immune cells. It is being developed by AstraZeneca/MedImmune for use in the treatment of cancer (MedImmune is a wholly owned subsidiary of AstraZeneca; AstraZeneca/MedImmune will be referred to as AstraZeneca throughout this document.) The proposed MOA for durvalumab is interference in the interaction of PD-L1 with PD-1 and CD80 (B7.1). Blockade of PD-L1/PD-1 and PD-L1/CD80 interactions releases the inhibition of immune responses, including those that may result in tumor elimination. In vitro studies demonstrate that durvalumab antagonizes the inhibitory effect of PD-L1 on primary human T cells, resulting in the restored proliferation of IFN $\gamma$  (Stewart et al 2015). In vivo studies have shown that durvalumab inhibits tumor growth in xenograft models via a T-cell-dependent mechanism (Stewart et al 2015). Based on these data, durvalumab is expected to stimulate the patient's antitumor immune response by binding to PD-L1 and shifting the balance toward an antitumor response. Durvalumab has been engineered to reduce antibody-dependent cellular cytotoxicity and complement-dependent cytotoxicity.

To date, durvalumab has been given to more than 6000 patients as part of ongoing studies either as monotherapy or in combination with other anticancer agents. Details on the safety profile of durvalumab monotherapy are summarized in Section 2.3.2 and Section 8.3.13.1. Refer to the current durvalumab IB for a complete summary of nonclinical and clinical information including safety, efficacy, and pharmacokinetics (PK).

Durvalumab has been approved to treat unresectable stage III non-small cell lung cancer, and extensive-stage small cell lung cancer (administered in combination with chemotherapy). Refer to the package insert (or label) for your specific country, as applicable.

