### 2.3.2.2 Risks

Monoclonal antibodies (mAbs) directed against immune checkpoint proteins, such as PD-L1 as well as those directed against PD-1 or cytotoxic T-lymphocyte antigen 4 (CTLA-4), aim to boost endogenous immune responses directed against tumor cells. By stimulating the immune system, however, there is the potential for adverse effects on normal tissues.

Most adverse drug reactions seen with the immune checkpoint inhibitor class of agents are thought to be due to the effects of inflammatory cells on specific tissues. These risks are generally events with a potential inflammatory or immune-mediated mechanism and which may require more frequent monitoring and/or unique interventions such as immunosuppressants and/or endocrine therapy. These immune-mediated effects can occur nearly in any organ system and are most commonly seen as gastrointestinal (GI) AEs such as colitis and diarrhea; pneumonitis/interstitial lung disease (ILD); hepatic AEs such as liver enzyme elevations; skin events such as rash, and dermatitis; and endocrinopathies including hypo- and hyper-thyroidism.

Risks with durvalumab include, but are not limited to, diarrhea/colitis, pneumonitis/ILD, endocrinopathies (ie, events of hypophysitis/hypopituitarism, adrenal insufficiency, hyper- and hypo-thyroidism, type I diabetes mellitus and diabetes insipidus), hepatitis/increases in transaminases, nephritis/increases in creatinine, , rash/dermatitis, myocarditis, myositis/polymyositis, infusion-related reactions, hypersensitivity reactions, pancreatitis, serious infections, and other rare or less frequent inflammatory events including neuromuscular toxicities (e.g. Guillain Barre syndrome, myasthenia gravis).

For information on all identified and potential risks with durvalumab, please always refer to the current version of the durvalumab IB.

In monotherapy clinical studies, AEs at an incidence of  $\geq 20\%$  include events such as fatigue, cough, decreased appetite, dyspnea and nausea. Approximately 10% of patients discontinued the drug due to an AE. Please see the current version of the IB for a detailed summary of the monotherapy data including AEs, SAEs, and CTC Grade 3 to 5 events reported across the durvalumab program.

The majority of treatment-related AEs were manageable with dose delays, symptomatic treatment, and, in the case of events suspected to have an immune basis, the use of established treatment guidelines for immune-mediated toxicity (see Section 8.4.5.1).

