### **2.3.4 Olaparib and durvalumab benefit/risk**

As noted in Section 2.1, the hypothesis to be tested in this study is that increased DNA damage triggered through PARP inhibition will result in enhanced antitumor immunity that can be further enhanced through combination with an immune checkpoint inhibitor in UC. Additionally, there is a strong correlation between olaparib and platinum sensitivity due to the underlying mechanisms surrounding platinum agents (cisplatin and carboplatin), PARP inhibition, and their correlation with tumor cells exhibiting DNA-repair gene mutations that lack effective and accurate mechanisms for DNA repair. While patients in this study are medically unfit for platinum therapies, the sensitivity of their tumors to PARP inhibition will be tested.

Encouraging clinical activity, combined with acceptable and manageable safety, has been seen to date with durvalumab in combination therapy studies. In general, the toxicity profiles of durvalumab and olaparib are non-overlapping. Pneumonitis is considered to be the most important potential exception. See Section 8.3.13.3 for the management guidelines for pneumonitis integrate the guidance provided for these 2 agents.

mAbs are not metabolized through classical hepatic enzyme pathways. Olaparib has previously been combined with another mAb (bevacizumab) without significant drug-drug interaction. Therefore, no PK interaction is anticipated within this study.

Clinical data on the tolerability and safety of durvalumab plus olaparib are emerging. A Phase I, dose escalation study reported that there were no dose-limiting toxicities for durvalumab plus olaparib in 12 female subjects with cancer. The most frequent treatment-emergent AEs were hematologic toxicities, including lymphopenia and anemia (Lee et al 2017). The combination of durvalumab plus olaparib is also being evaluated in several tumor types (MEDIOLA; NCT02734004) with reported safety data in small cell lung cancer. The most frequent Grade 3 and higher AEs in this study were anemia (39.5%) and lymphopenia (13.2%). The majority of other AEs could be attributed to underlying disease (Krebs et al 2017). Thus far, treatment-related AEs for durvalumab

plus olaparib have been consistent across studies and indications, with no evidence of an increase in frequency or severity of immune-mediated adverse events (imAEs).

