## **B 7 A guide to interpreting the causality question**

When making an assessment of causality, consider the following factors when deciding if there is a “reasonable possibility” that an AE may have been caused by the drug:

- Time course. Exposure to suspect drug. Has the patient actually received the suspect drug? Did the AE occur in a reasonable temporal relationship to the administration of the suspect drug?
- Consistency with known drug profile. Was the AE consistent with the previous knowledge of the suspect drug (pharmacology and toxicology) or drugs of the same pharmacological class, or could the AE be anticipated from its pharmacological properties?
- De-challenge experience. Did the AE resolve or improve on stopping or reducing the dose of the suspect drug?
- No alternative cause. The AE cannot be reasonably explained by another etiology such as the underlying disease, other drugs, other host or environmental factors.
- Re-challenge experience. Did the AE reoccur if the suspected drug was reintroduced after having been stopped? AstraZeneca would not normally recommend or support a re-challenge.

- Laboratory tests. A specific laboratory investigation (if performed) has confirmed the relationship.

In difficult cases, other factors could be considered such as the following:

- Is this a recognized feature of overdose of the drug?
- Is there a known mechanism?

Causality of “related” is made if following a review of the relevant data, there is evidence for a “reasonable possibility” of a causal relationship for the individual case. The expression “reasonable possibility” of a causal relationship is meant to convey, in general, that there are facts (evidence) or arguments to suggest a causal relationship.

The causality assessment is performed based on the available data including enough information to make an informed judgment. With limited or insufficient information in the case, it is likely that the event(s) will be assessed as “not related.”

Causal relationship in cases where the disease under study has deteriorated due to lack of effect should be classified as no reasonable possibility.

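### Section 8.3.13.3 says pneumonitis has not been seen with anti-PD-L1 antibodies, which contradicts the protocol's own durvalumab risk and AESI lists and could tilt causality ratings

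*Protocol*

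**What the plan says.** Protocol 8.3.13.3 (Pneumonitis) explains the sponsor's interest in the event by saying that "pneumonitis has been observed with use of anti-PD-1 mAbs (although not with anti-PD-L1 mAbs"), and adds that cases have been reported in patients taking olaparib.

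Elsewhere the current protocol says:

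- 2.2.2 (Durvalumab): the drug "blocks the interaction of PD-L1 (but not programmed cell death ligand 2 [PD-L2]) with PD-1 on T cells". It is therefore within the class that 8.3.13.3 exempts.
- 8.3.13.1 (AESIs for durvalumab): "AESIs observed with anti PD-L/PD-1 agents such as durvalumab include pneumonitis, hepatitis, diarrhea/colitis, intestinal perforation".
- 2.3.2.2 (Risks): "Risks with durvalumab include, but are not limited to, diarrhea/colitis, pneumonitis/ILD, endocrinopathies".
- 2.3.4 (Olaparib and durvalumab benefit/risk): the two toxicity profiles are described as generally non-overlapping, but "Pneumonitis is considered to be the most important potential exception". The reader is then referred to 8.3.13.3.
- Appendix B 7, among the factors for judging causality: "Was the AE consistent with the previous knowledge of the suspect drug".

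**The concern.** Section 8.3.13.3 is the designated text for the one toxicity that the protocol singles out as potentially shared by both drugs. Its opening paragraph tells the investigator that the antibody class given to every patient has not been associated with the event, and that the tablet has. An investigator who takes this as the known drug profile has a reason to rate durvalumab as not causal.

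Three provisions make the rating matter:

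- Under 8.3.4 the investigator records causality against the investigational products.
- Under 8.4.5.1 the durvalumab toxicity guidelines apply to events that the investigator considers related to durvalumab.
- Under 7.1 one agent may be stopped without the other only for treatment-related toxicity.

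Both arms receive durvalumab under a double blind. In the durvalumab + placebo arm (75 of the planned 150 patients), a case moved away from durvalumab could be attributed to a tablet that is placebo. At stake are the related-event rating and the attribution to a particular drug.

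**Working it through.** No arithmetic applies: the point rests on no error rate, power figure or event count. The check is whether the statements can be read together, and then what depends on them.

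**Step 1: does the exemption in 8.3.13.3 cover durvalumab?** Yes. Section 2.2.2 describes durvalumab as an antibody that blocks PD-L1, and 8.4.5.1 calls it a PD-L1 inhibitor.

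**Step 2: can the statements be reconciled?**

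| Section | Pneumonitis with durvalumab or its class |
|---|---|
| 8.3.13.3 | Not observed with anti-PD-L1 antibodies |
| 8.3.13.1 | Observed; first in the AESI list |
| 2.3.2.2 | Listed as a risk, together with ILD |
| Table 6 (EGFR TKIs) | Increased incidence reported when durvalumab was given with third-generation EGFR TKIs |

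A risk list alone might be read as precautionary. Section 8.3.13.1 cannot be, because it speaks of events observed and gives durvalumab as the example. Table 6 is weaker evidence, since a second drug is involved, but it points the same way.

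**Step 3: is the statement in operative text?** Yes. It is current body text, not an entry in the version history. Section 2.3.4 and the pulmonary-symptoms guidance in 8.4.5.2 both refer the reader to 8.3.13.3.

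**Step 4: can it reach the data?** Appendix B 7 lists six main factors for causality. Consistency with the known profile of the drug, or of its class, is one of them, and the parenthesis supplies a class statement for that factor. The resulting rating feeds 8.3.4, 8.4.5.1 and 7.1.

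**Step 5: what limits the effect?**

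- 8.3.13.3 itself asks for immune-related and other processes to be considered in the differential diagnosis, and points to the toxicity guidelines for immune-related pneumonitis.
- 8.4.5 and 8.4.5.1 treat events without a clear alternative cause as potentially immune related.
- 8.3.13.2 requires every pneumonitis event to be reported on SAE timelines whatever the causality rating.

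The exposed quantity is therefore the causality rating and the attribution by drug. The count of cases is protected.

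**The case against.** The strongest reply is that the parenthesis is a background remark, surrounded by text that corrects it. Much of this stands.

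- **Immune-mediated classification.** A reader might infer that investigators would stop classing pneumonitis as immune-mediated. The documents do not support that: 8.3.13.3, 8.4.5 and 8.4.5.1 all keep an immune cause in view, and 8.3.13.1 refers doubtful cases to the Study Physician.
- **Every case affected.** A reader might also infer that the classification of every pneumonitis case is distorted. At most, cases are exposed where an investigator gives this clause more weight than 2.3.2.2, 8.3.13.1, 8.4.5 and the Investigator's Brochure.
- **Role of B 7.** Drug profile is one factor among several, so B 7 does not make the parenthesis decisive. Section 2.3.3.2 also says that the evidence does not support a causal link between olaparib and pneumonitis, which works against a simple shift towards the tablet.
- **Rating per drug.** Sections 8.3.4 and 8.3.5 do not say that each agent is rated separately. If one rating covers the regimen, moving attribution from one drug to the other would leave the count of related events unchanged.
- **Stopping treatment.** For unexplained pulmonary symptoms, 8.3.13.3 recommends interrupting study treatment, which Section 6 defines to include all products. Significant abnormalities go to the Study Physician. The parenthesis is not itself a stopping rule.
- **Origin of the error.** It is tempting to conclude that the clause was left behind when other sections were updated in Version 3.0. The version history names Section 8.3.13 as a whole among the updates, so this remains an inference.

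None of these points removes the contradiction. Reporting regardless of causality protects capture; it does not correct a rating that rests on a wrong premise.

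**Conclusion.** The contradiction is established on the text. Section 8.3.13.3 cannot be squared with 8.3.13.1 or 2.3.2.2 on whether pneumonitis occurs with durvalumab's class.

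The consequence is a possible bias in the investigator's causality rating, away from durvalumab and towards olaparib/placebo. It assumes that some investigators rely on the section to which they are directed; for effects on drug-specific tabulations, it also assumes that causality is recorded separately by agent. Its size cannot be given, because the documents state no pneumonitis rate. Case capture, PFS and the sample size are untouched.

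This is a limited but real defect in safety guidance about a study drug, and it should be corrected.

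**What to change.** Reconcile the risk statement in 8.3.13.3 with 2.3.2.2 and 8.3.13.1, so that causality is judged on one consistent statement of what is known about each drug. One way is to replace the parenthesis with a cross-reference to the AESI list in 8.3.13.1.

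The change alters no dose, interruption, discontinuation or management rule. It costs one clause in the next amendment.

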## 8.4 Safety reporting and medical management

### 8.4.1 Reporting of serious adverse events

All SAEs have to be reported, whether or not considered causally related to the IP, or to the study procedure(s). All SAEs will be recorded in the eCRF.

If any SAE occurs in the course of the study, then Investigators or other site personnel will inform the appropriate AstraZeneca representatives within 1 day, ie, immediately but **no later than 24 hours** of when he/she becomes aware of it.

The designated AstraZeneca representative works with the Investigator to ensure that all the necessary information is provided to the AstraZeneca Patient Safety data entry site **within 1 calendar day** of initial receipt for fatal and life-threatening events **and within 5 calendar days** of initial receipt for all other SAEs.

For fatal or life-threatening AEs where important or relevant information is missing, active follow-up is undertaken immediately. Investigators or other site personnel will inform AstraZeneca representatives of any follow-up information on a previously reported SAE within 1 calendar day, ie, immediately but **no later than 24 hours** of when he/she becomes aware of it.

Once the Investigators or other site personnel indicate an AE is serious in the WBDC system, an automated email alert is sent to the designated AstraZeneca representative.

If the WBDC system is not available, then the Investigator or other study site personnel reports an SAE to the appropriate AstraZeneca representative by telephone.

The AstraZeneca representative will advise the Investigator/study site personnel how to proceed.

The Principal Investigator is responsible for ensuring that procedures and expertise are available to handle medical emergencies during the study. **A medical emergency usually constitutes an SAE and is to be reported as such.**

For further guidance on the definition of an SAE, see [Appendix B](#).

